#### **6.5.1 Data Collection and Follow-up for Withdrawn Subjects**

Subjects who withdraw consent to participate in the study will be seen for one final visit, during which they will be asked for permission to have the study team look into their survival status via publically available means.

#### **6.6 Early Termination Visits**

If a subject decides to leave the study early or is asked by the investigator to cease participation in the study, an early termination visit will include all of the items indicated for the planned final visit.

### **7 Study Evaluations and Measurements**

#### **7.1 Physical Examination**

The investigator or qualified designee will perform a complete physical exam during the screening period. Clinically significant abnormal findings should be recorded as medical history. For cycles that do not require a full physical exam per the Trial Flow Chart, the investigator or qualified designee will perform a directed physical exam as clinically indicated prior to trial treatment administration.

#### **7.2 Vital Signs**

The investigator or qualified designee will take vital signs at screening, prior to the administration of each dose of trial treatment and at treatment discontinuation as specified in the Trial Flow Chart. Vital signs should include temperature, pulse, respiratory rate, weight and blood pressure. Height will be measured at screening only.

#### **7.3 Pregnancy Testing**

Females of childbearing potential must have a negative serum or urine beta human chorionic gonadotropin ( $\beta$ -hCG) pregnancy test result within 15 days prior to the starting radiation therapy and must agree to use an effective contraception method during the study and for 6 months following the last dose of nivolumab; females of non-childbearing potential are those who are post-menopausal for more than 1 year or who have had a bilateral tubal ligation or hysterectomy. Female patients undergoing active fertility preservation therapy/egg harvesting which include hCG injections are expected to have mild elevation of hCG. These patients may be allowed to participate in the trial despite elevation of hCG after providing documentation of negative hCG prior the hCG injection and statement from her fertility specialist that they are not pregnant. Males who have partners of childbearing potential must agree to use an effective contraceptive method during the study and for 6 months following the last dose of study drug.

#### **7.4 Efficacy Evaluations**

Efficacy will be evaluated based on the Response Criteria described in Section 6.3.26.3.1

CONFIDENTIAL

## **7.5 Safety Evaluations**

Safety will be assessed based on the above-described physical examination, vital signs, and laboratory evaluations.

## **8 Statistical Design**

This is a single arm Phase II clinical trial for relapsed/refractory Hodgkin lymphoma patients receiving nivolumab followed by either: a) continued nivolumab monotherapy if patient achieves an induction complete response (CR) scored at week 8, or b) RT (4 Gy x 2 fractions) plus continued nivolumab for patients who achieve <CR after induction. In the RT group, a second response assessment is undertaken at week 16, to determine the number of patients who have achieved CR. In both groups, nivolumab is continued until disease progression, drug intolerance, or at the discretion of the treating medical oncologist. continued until disease progression, drug intolerance, or at the discretion of the treating medical oncologist.

### **8.1 Primary Objective**

1. To determine the overall complete response (CR) rate for the study.

### **8.2 Secondary Objectives**

1. To determine the nivolumab induction CR rate
2. To determine the post-RT + continued nivolumab CR rate
3. To determine the time to best response
4. To determine duration of best response
5. To estimate progression free survival, overall survival and disease free survival
6. To evaluate safety and adverse events

### **8.3 Exploratory Objectives**

1. To evaluate baseline and post-treatment changes in biomarkers and determine whether biomarker changes are associated with clinical outcomes.
2. To evaluate tumor FDG uptake and determine whether FDG "flare" is associated with clinical outcomes.

### **8.4 Primary Endpoint**

The primary endpoint is the overall CR rate, defined as the total number of CRs after nivolumab induction, plus the total number of CRs after RT + continued nivolumab in those patients with <CR after induction, divided by the total number of patients treated on the study. The Cheson criteria will be used to score response.

### **8.5 Secondary Endpoints**

1. The nivolumab induction CR rate is defined as the proportion of patients who achieve CR after nivolumab induction, at the week 8 evaluation.
2. The post-RT + continued nivolumab CR rate is defined as the proportion of patients who achieve CR after RT + continued nivolumab, at the week 16 evaluation (8-12 weeks post-RT). All patients who had <CR are eligible to receive RT. The denominator will include all eligible patients, regardless of whether 2 fractions of RT were administered.
3. Time to best response is defined from date of study entry to date of best response. For progressive disease patients, time to best response will be defined from study entry to date taken off study due to PD. It is assumed that most patients who are scored PD at 8-12 weeks, will continue nivolumab for another 8 weeks.
4. Duration of best response is defined from date of best response to date of disease progression, death due to any cause of last patient contact alive and progression-free.
5. Progression free survival is defined from date of study entry to date of disease progression, death due to any cause of last patient contact alive and progression-free.
6. Overall survival is defined from date of study entry to date of death due to any cause of last patient contact alive.

CONFIDENTIAL

7. Disease-free survival is defined from date of CR to date of disease progression, death due to any cause of last patient contact alive and disease-free. DFS is only computed for CR patients.
8. Toxicities will be graded and tabled separately by induction or post-RT.

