### 3.1.2 Study Intervention Phase

Nivolumab 3 mg/kg will be administered on day 1 (pre-response assessment week 0) and on day 1 and continued per standard of care and institutional practices. At the week 1 biomarker collection, research FDG PET/CT will be performed to assess for FDG "flare." At week 8-12, PET/CT will be performed for the first response assessment. If a complete anatomic response is seen, nivolumab monotherapy will be continued on day 1 and continued per standard of care and institutional practices.

By contrast, if at week 8 less than a complete anatomic response is seen, radiotherapy to 4 Gy x 2 fractions will be administered (post-response assessment week 0). The patient will be evaluated by a radiation oncologist while on treatment, and toxicities will be recorded. Nivolumab will be continued on day 1 and continued per standard of care and institutional practices.

In either scenario, a second response assessment will be conducted ~8-12 weeks after the first response assessment. In either scenario, nivolumab monotherapy will be continued at the discretion of the treating medical oncologist.

If there is less than CR post-RT and there is an additional untreated non-target lesion that can be followed, radiotherapy can again be administered when disease progresses to a previously untreated lesion, after which the patient will continue on the post-RT follow-up algorithm.

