#### **4.4 Duration of Study Participation**

The duration of the study is approximately 22-25 weeks, from the time of pre-trial assessment through the final end-of-study visit. The duration of the intervention phase of the study is approximately 20-23 weeks: 8-12 weeks for nivolumab monotherapy, 8-12 weeks for continued nivolumab monotherapy vs. RT plus nivolumab, with 3 weeks allowed for RT simulation and planning. An additional 8-12 weeks is appended for patients undergoing additional RT.

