- **Response assessment:** At weeks 8-12 after the start of nivolumab, FDG PET/CT will be obtained for response assessment. For patients undergoing radiotherapy, an additional FDG PET/CT will be obtained at weeks 8-12 after the delivery of radiation. Subsequent FDG PET/CT(s) will be obtained as clinically indicated in follow-up.

Adverse events that are grade 3 or higher will be recorded post injection of the radiotracer to the completion of the imaging exam.

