### 6.3.3 End of Study Visit

At the end of study visit – the second response assessment, 8-12 weeks after the first response assessment – FDG-PET will be performed, the patient will be evaluated for toxicities, and a final blood draw will be taken for correlative biomarkers. Patient charts will be reviewed for progression, response, and overall survival.

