#### **8.8 Plans for Data Analysis**

1. Baseline and demographic characteristics will be summarized by standard descriptive statistics (including mean and standard deviation for continuous variables such as age and frequency and percentage for categorical variables such as gender).
2. The overall CR rate and 95% exact confidence interval will be calculated. Following an intent to treat analysis, all patients who received at least 1 dose of nivolumab are included in the analysis of the primary endpoint. Based on an exact binomial test, the number of patients with CR will determine whether the null hypothesis will be rejected (see Sample Size/Power below).
3. The nivolumab induction CR rate and post-RT + continued nivolumab CR rate and 95% confidence intervals will also be calculated.
4. Time to best response and duration of best response will be calculated and summarized separately for CR, PR, SD and PD patients.
5. Progression free survival, overall survival and disease-free survival will be estimated by the Kaplan-Meier method. Disease free survival will be computed by landmark analysis for two distinct groups: 1) DFS from week 8, for patients who achieved induction CR and 2) DFS from week 16, for patients who achieved CR after RT + nivolumab.
6. All subjects entered into the study will have detailed information collected on adverse events for the overall study safety analysis. Toxicities will be graded and tabled separately by induction nivolumab, post-induction nivolumab or post-induction RT + continued nivolumab.

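### The post-radiotherapy response scan has three different time anchors, and Section 8.8 starts disease-free survival at fixed weeks 8 and 16 although Section 8.5 starts it when CR is reached

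*Combined protocol and SAP*

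**What the plan says.** For patients with less than CR after induction, the timing of the second response assessment is given in three ways.

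- **From the first scan.** Section 3.1.2: "a second response assessment will be conducted ~8-12 weeks after the first response assessment". Section 6.3.3 repeats this for the end-of-study visit: "the second response assessment, 8-12 weeks after the first response assessment".
- **From radiotherapy.** Section 6.2.2: "an additional FDG PET/CT will be obtained at weeks 8-12 after the delivery of radiation".
- **At a fixed study week.** The opening of Section 8 puts the second assessment of the radiotherapy group at week 16. Item 2 of Section 8.5 equates that week with the radiotherapy window: "at the week 16 evaluation (8-12 weeks post-RT").

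The first scan is also described in two ways. Section 3.1.2 has a window: "At week 8-12, PET/CT will be performed for the first response assessment". Item 1 of Section 8.5 has a single week: "proportion of patients who achieve CR after nivolumab induction, at the week 8 evaluation".

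For DFS, item 7 of Section 8.5 takes the date of CR as time zero. Item 5 of Section 8.8 instead uses fixed landmarks: week 8 for induction CRs, and for the others "DFS from week 16, for patients who achieved CR after RT + nivolumab".

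The file holds two copies of the protocol, and both carry the same text on these points.

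**The concern.** A response assessed some weeks after treatment depends on when one looks. Section 1.5 itself notes that morphological change under immunotherapy can take several months to appear. If the sections give different dates for the scan, staff following different sections could scan the same patient at different times.

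The post-radiotherapy CRs matter to the primary endpoint. Section 8.4 adds them to the induction CRs without attaching a time. Section 4.5 expects an induction CR rate of about 10%, which is 0.10 × 25 = 2.5 patients, while Section 8.9 requires 6 CRs to reject the null hypothesis.

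The DFS conflict is more direct. A patient can enter the post-radiotherapy CR group only by being alive and found in CR at the second scan. If the clock starts at week 16 and the scan comes later, the weeks in between are event-free by construction and lengthen the reported DFS.

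**Working it through.** **Inputs**

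- F, study week of the first scan: 8 to 12 (Section 3.1.2).
- d, delay from first scan to radiotherapy: 0 to 3 weeks. This range is an assumption. Section 4.4 gives only the 3-week allowance and no minimum.
- w, length of the window to the second scan: 8 to 12 weeks (Sections 3.1.2, 6.2.2, 6.3.3).
- Study weeks are counted from the start of nivolumab. The 2 to 4 days of radiotherapy (Section 5.2.5) are ignored; 4/7 is about 0.6 week.

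**Can the plan's own equation be reproduced?** Section 8.5 sets week 16 equal to 8 to 12 weeks post-radiotherapy. Counting from radiotherapy, the scan falls at week F + d + w, whose minimum is 8 + 0 + 8 = 16. The equation therefore holds only when F = 8, d = 0 and w = 8. If the full 3 weeks are used, the earliest scan 8 weeks after radiotherapy is at week 8 + 3 + 8 = 19.

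**Consequences of each anchor**

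| Anchor | Study week of second scan | Weeks from radiotherapy to scan |
|---|---|---|
| First scan | F + w: 8 + 8 = 16 to 12 + 12 = 24 | w − d: 8 − 3 = 5 to 12 − 0 = 12 |
| Radiotherapy | F + d + w: 8 + 0 + 8 = 16 to 12 + 3 + 12 = 27 | w: 8 to 12 |
| Literal week 16 | 16 | 16 − F − d: 16 − 12 − 3 = 1 to 16 − 8 − 0 = 8 |

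**Do the first two anchors conflict?** Not entirely. In weeks after the first scan, one window is 8 to 12 and the other is 8 + d to 12 + d. They share 8 + d to 12, which is 11 to 12 weeks when d = 3. A scan in that overlap satisfies both.

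**DFS start against the date CR can first be seen**

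- Induction CR: landmark week 8, scan as late as week 12, so up to 12 − 8 = 4 weeks too early.
- Post-radiotherapy CR, first-scan anchor: scan as late as week 24, so up to 24 − 16 = 8 weeks.
- Post-radiotherapy CR, radiotherapy anchor: scan as late as week 27, so up to 27 − 16 = 11 weeks.

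These are maxima with every window at its upper end. At the lower ends (F = 8, d = 0, w = 8) the excess is zero.

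**Decision rule.** An exact binomial check with 25 patients, rejection at 6 or more CRs, and rates of 10% and 30% gives a one-sided level of 0.0334 and power of 0.8065. These agree with the 3% and 81% in Section 8.9. No timing enters this calculation.

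**The case against.** The strongest reply is that the sections can be read together. Section 3.1.2 and Section 6.3.3 must also serve patients who receive no radiotherapy and so have no radiotherapy date. Section 6.2.2 could be the specific rule for those who do. Section 3.1.2 labels radiotherapy as post-response week 0, and the Section 6 schedule follows that numbering. Weeks 8 and 16 would then be nominal labels, just as week 8 evidently stands for a scan allowed up to week 12. This is plausible, and it explains how the text may have arisen. But no section says which rule prevails or that the weeks are nominal, and Section 8.8 uses them as time origins.

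It can also be said that DFS is already correctly defined in item 7 of Section 8.5. That is so. The defect is that Section 8.8 contradicts that definition, and an analyst following Section 8.8 would use the wrong time zero.

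A reader might infer more than the documents support:

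- **That one patient could be scanned both 5 weeks after radiotherapy and at week 27.** The two figures belong to different anchors. With the first-scan anchor the latest scan is week 24; with the radiotherapy anchor the interval is never below 8 weeks.
- **That all three timings exclude each other.** The two 8-to-12-week windows overlap, and for a scan at the same point in its window they differ by d, at most 3 weeks. Only literal week 16 fails to fit, outside the one corner case.
- **That the primary result is biased.** Section 8.4 names no week, and no figure in the documents shows how many CRs would change with the scan date.
- **That the intervention phase in Section 4.4 is miscalculated.** Its parts do span 8 + 8 + 3 = 19 to 12 + 12 + 3 = 27 weeks, whereas the section says "The duration of the intervention phase of the study is approximately 20-23 weeks". But the figure is approximate. Window midpoints give 10 + 10 = 20 without planning time and 23 with it (an inference; the section does not explain it), and no analysis uses the figure.

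**Conclusion.** The point holds in two parts. First, the second assessment of irradiated patients lacks a single time anchor, and equating week 16 with 8 to 12 weeks post-radiotherapy is true only if the first scan is at week 8, radiotherapy is immediate and the second scan is exactly 8 weeks later. Second, and firmly, item 5 of Section 8.8 contradicts item 7 of Section 8.5 on when DFS begins. Read literally, Section 8.8 credits event-free time before CR was observed: up to 4 weeks for induction CRs, and up to 8 weeks (first-scan anchor) or 11 weeks (radiotherapy anchor) for post-radiotherapy CRs.

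The sizes that involve radiotherapy timing rest on the assumed delay of 0 to 3 weeks; the 4-week and 8-week figures do not depend on it. DFS is a secondary endpoint. Consistent scan timing is also desirable for the primary endpoint, but its effect on the CR count is not quantified, and power and the 6-of-25 rule stand as stated.

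**What to change.** 1. Reconcile Sections 3.1.2, 6.2.2, 6.3.3, the opening of Section 8 and item 2 of Section 8.5 to one anchor and one window for irradiated patients, and state what applies to patients without radiotherapy. The documents do not show which anchor is intended, so that choice is left to the investigators.
2. Amend item 5 of Section 8.8 so that DFS starts at the actual date of the scan documenting CR, in line with item 7 of Section 8.5, for both CR groups.
3. State that week 8 and week 16 are nominal labels for the first and second assessments wherever they occur, including the marker-change comparisons in the exploratory analyses.

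The cost is a wording amendment. No scan or patient is added, and the analysis needs only the dates of scans already planned.

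### Duration of best response can only be zero or negative when best response is PD, and no method is named for its censored values

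*Combined protocol and SAP*

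**What the plan says.** Time to and duration of best response are named secondary objectives (Sections 2.2 and 8.2).

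- Section 8.5 item 3 gives the general rule: "Time to best response is defined from date of study entry to date of best response".
- The same item adds a rule for PD: "For progressive disease patients, time to best response will be defined from study entry to date taken off study due to PD". It then states: "It is assumed that most patients who are scored PD at 8-12 weeks, will continue nivolumab for another 8 weeks".
- Section 8.5 item 4 sets the interval: "Duration of best response is defined from date of best response to date of disease progression". The alternative ends are death and "last patient contact alive and progression-free" (reading the printed *of* before these words as *or*).
- Section 8.8 item 4 sets the analysis: "Time to best response and duration of best response will be calculated and summarized separately for CR, PR, SD and PD patients".
- Section 8.8 item 5 names the survival method: "Progression free survival, overall survival and disease-free survival will be estimated by the Kaplan-Meier method". Duration of best response is not listed.

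The document prints the protocol twice, and these items read the same in both copies.

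**The concern.** There are two separate problems.

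First, items 3 and 4 of Section 8.5 do not work together for PD. Item 3 moves the best-response date to the day the patient leaves the study because of PD. Item 4 starts the clock there and stops it at progression, which has already happened. Section 8.8 nevertheless asks for this quantity in a PD row. An analyst who follows the text must print zeros or negative durations, or else invent an unplanned rule.

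Second, duration is defined with an end at last contact for patients who have not progressed, so it is a censored time. The plan names a method for censored data for PFS, OS and DFS but not for duration. If the analyst takes an ordinary median or mean, a patient still in response counts as if the response had ended at last contact, and duration comes out too short.

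Both affect the reporting of a secondary descriptive endpoint. The primary analysis is not involved.

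**Working it through.** **PD row.** Inputs are the dating rules in Section 8.5 items 3 and 4, PD scored at week 8 or 12, and removal 0 or 8 weeks later (the 8 weeks is item 3's own assumption). I take study entry as week 0 and date progression at the first PD score.

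Time to best response = off-study date - entry. Duration = progression date - best-response date, with the off-study date as best-response date.

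| PD scored | Off study | Time to best response | Duration |
|---|---|---|---|
| week 8 | week 8 | 8 weeks | 8 - 8 = 0 |
| week 8 | week 16 | 16 weeks | 8 - 16 = -8 weeks |
| week 12 | week 12 | 12 weeks | 12 - 12 = 0 |
| week 12 | week 20 | 20 weeks | 12 - 20 = -8 weeks |

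If progression is dated at removal, or best response is dated at the PD score, the duration is 0 in every line. No reading gives a positive value. This applies to patients whose *best* response is PD. A patient scored PD who later responds belongs in another row.

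**How many patients.** Section 1.2 cites 9% CR, 58% PR and 23% SD on monotherapy. The remainder is 100 - 9 - 58 - 23 = 10%, and 0.10 × 25 = 2.5 patients. This is an upper figure, because the remainder may include unevaluable patients.

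**Censoring.** The plan gives no figure for duration to reproduce. Section 1.2 cites a 6-month PFS of 76.9%. If that applied here, 0.769 × 25 = 19.2, so about 19 of 25 patients would be progression-free at six months, close to the end-of-study visit at 22-25 weeks (Section 4.4). The final share censored cannot be derived from the documents.

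To show the size of a possible bias, I assume exponential durations and uniform censoring times. These assumptions are not in the documents. The table gives medians in months from large simulated samples: the plain median that treats censored times as complete, then Kaplan-Meier.

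| True median | Censoring 0-22 months | Censoring 6-22 months | Censoring 0-12 months |
|---|---|---|---|
| 6 | 4.2; 6.0 | 6.0; 6.0 | 3.3; 6.0 |
| 12 | 6.2; 12.0 | 8.7; 12.0 | 4.3; not reached |
| 18 | 7.4; 18.0 | 10.2; 18.0 | 4.8; not reached |

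The share censored runs from 23% (true median 6, censoring 6-22 months) to 80% (true median 18, censoring 0-12 months). The bias is nil in the first of these settings and large in the second.

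**Which rows are exposed.** Section 8.5 item 7 runs DFS from the date of CR to progression, death or last contact. For a CR patient that is essentially the duration of best response, and Section 8.8 item 5 estimates it by Kaplan-Meier, with landmarks at weeks 8 and 16. The rows without such cover are PR and SD.

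**Design figures.** With 25 patients and rejection at 6 or more CRs, the exact binomial gives power 0.8065 at 30% and a one-sided level of 0.0334 at 10%. These match the 81% and 3% in Section 8.9. Duration does not enter this calculation.

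**The case against.** The best defence is that this is under-specification in one descriptive table. A negative duration would be noticed at once. Item 3's PD rule was written for time to best response, and the plan does not say outright that it also sets the start of duration. That much is fair, but without the PD rule the value is still zero, so the PD row carries no information either way.

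Several stronger readings are tempting, and the documents do not support them:

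- *Time to best response is also impossible for PD patients.* It is positive (8 to 20 weeks in the table). The fault is that it measures time to removal from study, not time to a response.
- *The plan treats censored durations as complete.* Section 8.8 item 4 says only that duration is calculated and summarized. It neither names nor rules out Kaplan-Meier, so the bias is a risk of the silence and not a stated method.
- *All responders are affected.* CR patients are already covered by DFS.
- *Continuing nivolumab after PD contradicts Section 8.* A reader might infer this from "nivolumab is continued until disease progression, drug intolerance" taken alone. The sentence goes on to allow the treating medical oncologist's discretion, and Sections 3.1 and 3.1.2 do the same. Section 3.1.2 also provides for further radiotherapy on progression. I raise no conflict here.
- *Duration should start at the first CR or PR.* The stated objective is duration of *best* response. For a patient with PR at week 8 and CR at week 16, starting at first response would add 8 weeks and replace the endpoint.

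**Conclusion.** The point holds as a defect in a secondary descriptive endpoint. For a patient whose best response is PD, the stated rules can give only zero or a negative duration. The figure of -8 weeks is the extreme, and needs progression dated at the first PD score and removal 8 weeks later. At most about 2-3 of 25 patients are involved, assuming the cited monotherapy mix carries over and the whole remainder is PD.

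The absence of duration from the Kaplan-Meier list is a gap in the plan. If it were filled by a plain summary, durations would tend to be too short, mainly in the PR and SD rows. The size of that bias depends on follow-up and true durations that the documents do not give. The primary CR test, its decision rule, the sample size and the power are unaffected.

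**What to change.** - **Section 8.5 items 3 and 4, and Section 8.8 item 4:** state that time to and duration of best response are not computed for patients whose best response is PD. Delete the PD dating rule in item 3 and describe these patients by PFS, which is already planned for the whole study population.
- **Section 8.5 item 4:** keep the start of duration at the date the best response is first documented, so the stated objective is preserved.
- **Section 8.8 item 5:** add duration of best response to the Kaplan-Meier list, with censoring at last contact alive and progression-free.
- **SD row:** keep it if wanted, since its durations are computable and not negative.

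The cost is a few sentences of wording and the PD row of one descriptive table. No visit, data item, sample size or power figure changes.
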